1.2.2. Randomization Methodology

Subjects who complete the study screening assessments and meet all eligibility criteria will be randomly assigned to receive either ELX-02 or placebo in a 2:1 ratio within each cohort. Within each cohort, up to 6 subjects will be randomized to receive ELX-02 and up to 3 subjects will be randomized to receive placebo for a total of up to 63 subjects. Treatment arm codes will be generated using a permuted block design. Each block will assign a 2:1 random allocation of ELX-02 or placebo using SAS® software. Each eligible subject will be assigned a unique on-study identification number. Two separate randomization schedules were created, one by SGS for Cohorts 1-6 and the other by Parexel for Cohort 7, as two separate EDC databases were created and used by these two vendors.

1.2.3. Removal, Replacement or Early Withdrawal

The Sponsor reserves the right to prematurely discontinue the study at any time for any reason. Subjects are free to discontinue their participation in the study at any time and without prejudice to further treatment. The Investigator must withdraw any subject from the study if that subject requests to be withdrawn, or if it is determined that continuing in the study would result in a safety risk to the subject. Subjects discontinued or withdrawn from the study after receiving ≤ 6 doses may be replaced upon request from the Sponsor. The subject's participation in this study may be discontinued due to the following reasons:

- Request by regulatory agency, Sponsor, primary care physician or Investigator
- Subject withdraws consent
- Female subject is pregnant
- Positive Urine Drug Screen (UDS) and/or serum alcohol test on admission to the CPU on Day -1. If subjects have a positive UDS and/or serum alcohol test after Day -1, their continued participation will be re-evaluated on a case by case basis
- AE or Serious Adverse Event (SAE) meeting criteria for drug-related event and meeting stopping criteria described in Protocol Section 3.2.
- Subject is unwilling or unable to continue the study or is lost-to-follow-up
- Subject is non-compliant with study procedures/study protocol
- Investigator decides that withdrawal from the study is in the best interest of the subject
- Subject needs medication not allowed in the protocol

- Any clinically significant change in subject's medical condition
- Subjects may be replaced at the discretion of the Sponsor

1.2.4. Breaking the Blind

Breaking the blind is expressly forbidden except in the event of a medical emergency where the identity of the study drug must be known in order to properly treat the subject. If breaking the blind is required because of a medical emergency, the treatment identity for the unblinded subject will only be revealed by the qualified designee with approval from the Sponsor's Medical Monitor or designee. Subjects who are unblinded for any reason during their participation in the study will not be replaced and will be withdrawn immediately from the study.

In the absence of a medical emergency, the blinded randomization for this study will not be revealed until all data are entered into the database, edits checks are performed, queries closed, electronic case report forms (eCRFs) signed by the principal investigator, and the database is officially locked.

The bioanalytical scientists and pharmacokineticists will be unblinded to treatment arm prior to database lock by having access to individual subject ELX-02 concentration data. The blind will be maintained to the clinical study team by transmitting only blinded PK summary tables and figures to the DSMB and the AVDSMB, and therefore there is no possibility of revealing individual subject treatment assignment.

1.2.5. Study Procedures

The schedule of assessments, as outlined in the study protocol, is provided in [Table 1](#).

Table 1 Schedule of Assessments

Day in Study	Hours Postdose	
	Informed consent ^a	Demographics
	Medical history ^b	
	Inclusion/exclusion criteria	
	Weight	Height, body mass index
		Vital signs ^d
		Physical examination ^e
		Blood safety lab tests ^f
		General urinalysis
		HIV, HbsAg, HCVAb
		Blood pregnancy + FSH (females)
		Urine pregnancy (females) ^g
		Urine drug screen (UDS)
		Serum alcohol test
		12-lead ECG ^h
		Audiometric testing ⁱ
		Vestibular Questionnaires (DHI, THI)
		Confinement to CPU ^j
		Discharge from CPU (2 hr after administration)
		Blood PK ^k
Day 2	24h	
Day 3	36h	
Day 4		
Day 7		
Day 8		
Day 10		
Day 11		
Day 14		
Day 15		
Day 17		
Day 18		
Day 21		
Day 22		

Day in Study	Hours Postdose	Assessments and Tests																											
		Informed consent ^a	Demographics	Medical history ^b	Inclusion/exclusion criteria	Weight	Height, body mass index	Vital signs ^d	Physical examination ^e	Blood safety lab tests ^f	General urinalysis	HIV, HbsAg, HCVAb	Blood pregnancy + FSH (females)	Urine pregnancy (females) ^g	Urine drug screen (UDS)	Serum alcohol test	12-lead ECG ^h	Audiometric testing ⁱ	Vestibular Questionnaires (DHI, THI)	Confinement to CPU ^j	Discharge from CPU (2 hr after administration)	Blood PK ^k	Urine collection for PK ^l	Urine collection for creatinine ^m	Dosing ⁿ	Local reaction of injection site	Urine for renal injury biomarkers ^m	Blood samples for retention ^o	Blood for housekeeping proteins
Day 24						X																							
Day 25						X		X																				X	
Day 28						X		X	X ^q	X			X	X	X			X									X		
Day 29	-180 min					X ^c		X									X	X ^p	X ^p									X	
	0																			X									X
	15 min																												X
	30 min							X																					X
	45 min							X																					X
	1 h							X																					X
	3h							X																					X
	6h								X	X ^q	X																	X	
	12h							X																					X
Day 30	24h					X		X ^q	X								X		X		X	X	X	X	X	X	X		

AE: Adverse event, CM: Concomitant therapy, HIV: Human Immunodeficiency Virus, HbsAg: Hepatitis B surface antigen, HCVAb: Hepatitis C virus antibody, CPU: Clinical Pharmacological Unit, DHI: Dizziness Handicap Inventory, THI: Tinnitus Handicap Inventory.

^a Informed consent to be provided before any study-related assessment.

^b Including hearing and balance disorders.

^c Weight only to be taken if not already done the previous day.

^d Vital signs include heart rate (HR), blood pressure (BP), respiratory rate (RR), and oral body temperature. Vital parameters will be assessed in supine position after at least 5 min. supine rest.

^e A complete physical examination is to be performed at all timepoints except for the 6h postdose assessment on Day 1 and Day 29 when a brief examination is to be performed.

^f Biochemistry, hematology, and coagulation. All blood samples for safety assessments should be taken after an overnight fast of at least 8h, except for the sample taken at 6h postdose on Day 1 and Day 29. At screening, subjects will be instructed not to eat within 3h before arrival at the CPU.

g Urine pregnancy tests only to be performed for women regardless of childbearing potential

h A single 12-lead ECG will be taken providing QT, QTc, HR, QRS and PR after 5 minutes supine

Subjects will be scheduled for audiometric and vestibular tests preceded by an ENT physical exam.

Subjects will be scheduled for audiometric and vestibular tests preceded by an ENT physical exam in a specialized department. The auditory and vestibular testing will be performed at

Screening (to confirm eligibility), and prior to initial dosing to determine a baseline and will include: (1) Otoscopy, (2) Immittance audiometry (commonly called tympanometry), (3) Speech Reception Threshold, (4) Pure Tone Audiometry (PTA) with frequencies up to 8 kHz if possible (should there be a PTA threshold of ≥ 15 dB, the subject should undergo bone conduction testing), (5) High frequency audiometry (HFA) with frequencies up to 16 kHz if possible, (6) Tinnitus Handicap Inventory, (7) Dizziness Handicap Inventory. Follow up testing will be performed at Day 3 (-1 day), Day 10 (-2 days), Day 17 (-2 days), Day 24 (-2 days), and EOS (7-11 days after last dosing). The otoscopic exam on Day 3, Day 10, Day 17 and Day 24 can be performed 72 hours prior to dosing by a CPU physician.

^j Subjects will come to the CPU for confinement on Day -1, Day 7, Day 14, Day 21, and Day 28.

^k The predose PK blood sample will be taken in a standardized manner for all subjects, right before study drug administration.

^l During the 0-12h collection period urine will be collected every hour, during the 12-24h collection period every 6h (i.e., 12-18h collection and 18-24h collection), and during the 24-48h collection period urine will be collected every 12h (i.e., 24-36h collection and 36-48h collection). Urine gravity will be calculated for each collection. The subjects will collect the urine at home (in urine jars) during the 48h-72h collection period.

^m Creatinine samples will be taken at all timepoints corresponding to renal injury biomarker collection. On days 1-4 and 29-32, samples for renal injury biomarkers and creatinine will be taken from urine spot samples at 24hr, 36hr, 48hr and 72hr post dose.

ⁿ Subjects should consume at least 500 mL of water within 120 minutes before dosing. Subcutaneous (SC) injection (s) in the abdominal wall as per the subject's body weight. The study staff will encourage the subjects to drink at least one glass (approximately 250 mL) of fluids every hour up to 10h after dosing.

^o All blood samples for retention need to be taken after an overnight fast of at least 8h, except for the samples taken at 3h postdose on Day 1 and Day 29.

^p Subject will return to the ENT specialist for auditory and vestibular tests within 48 hours prior to dosing. The otoscopic exam on Day 3, Day 10, Day 17 and Day 24 can be performed 72 hours prior to dosing by a CPU physician.

^q No GFR/MDRD sample/analysis beyond the screening period.

1.2.6. Efficacy, Pharmacokinetic, and Safety Parameters

1.2.6.1. Efficacy Parameters

This study does not assess efficacy.

1.2.6.2. Pharmacokinetic Endpoints and Parameters

The primary PK endpoint is to characterize plasma and urine PK of ELX-02.

The secondary PK endpoint is to determine the dose proportionality of plasma ELX-02 exposure across the administered SC dose range.

The PK parameters that will be calculated are provided in [Section 4.3](#).

1.2.6.3. Safety Endpoints and Parameters

The primary safety endpoint is to characterize the incidence of AEs and other changes in safety parameters at ascending doses.

The secondary safety endpoint is to assess, based on the safety profile, whether dose-limiting toxicity (DLT) and MTD are attained within the tested ELX-02 dose range.

Safety evaluations performed during the study include auditory and vestibular assessments, questionnaires, ear, nose and throat physical examinations, measurement of vital signs, 12-lead electrocardiograms (ECGs), clinical laboratory evaluations (hematology, serum chemistry, urinalysis, and coagulation), and monitoring of AEs (including adverse events of interest (AEOIs), injection site reactions (ISRs), and treatment discontinuations due to AE), DLTs, and concomitant medications.

2. SUBJECT POPULATION

2.1. Population Definitions

The following subject populations will be evaluated and used for presentation and analysis of the data:

- Pharmacokinetic (PK) Population: All subjects who are randomized, receive any amount of study drug, have at least 1 evaluable PK assessment, and have no relevant deviation interfering with the PK evaluations.
- Safety Population: All subjects who are randomized and receive any amount of study drug.

The PK population is the primary population for the analysis of PK parameters. The safety population is the primary population for the analysis of safety parameters.

2.2. Protocol Deviations

Protocol deviations will be presented in a data listing.

3. GENERAL STATISTICAL METHODS

3.1. Sample Size Justification

No formal sample size estimations were performed. The planned sample size of 9 subjects per dose group with a total of up to 63 subjects was considered sufficient to address the safety, tolerability and PK objectives of this study.

3.2. General Methods

All data listings that contain an evaluation date will contain a relative study day (Rel Day). Pre-treatment and on-treatment study days are numbered relative to the day of the first dose of study drug which is designated as Day 1. The preceding day is Day -1, the day before that is Day -2, etc.

All output will be incorporated into Microsoft Word RTF or Adobe Acrobat PDF files, sorted and labeled according to the International Council on Harmonisation (ICH) recommendations, and formatted to the appropriate page size(s).

Tabulations will be produced for appropriate demographic, baseline, PK, and safety parameters. For categorical variables, summary tabulations of the number and percentage of subjects within each category (with a category for missing data) of the parameter will be presented. For continuous variables, the number of subjects, mean, median, standard deviation (SD), minimum, and maximum values will be presented.

Summary tabulations for general and safety analyses will be presented by treatment and dose (including placebo, all dose levels and all ELX-02) and separately by concentration (including Cohorts 3, 4, 5 and 6). Placebo will be pooled across cohorts and presented in one column. A total column for those receiving ELX-02, regardless of dose, will also be included. The placebo and the total columns will not be included in the summary tabulations for PK analyses.

Figures for PK concentrations will be presented by cohort and figures for PK parameters will be presented by dose. If differences in PK parameters (AUC, C_{max} , $t_{1/2}$) between final diluted injection concentrations are observed in the “by concentration” summary tables, figures for PK parameters will be presented by cohort. Details for figure presentation are described in [Section 4.3.3](#).

All data listings will be presented by cohort.

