### 3. STUDY DESIGN

#### 3.1. Overall Study Design

This is a Phase 1, randomized, double-blinded, placebo-controlled, third party open, multiple dose escalation study to evaluate the safety, tolerability and PK of subcutaneously administered ELX-02 in independent consecutive cohorts of healthy subjects.

The investigational drug, ELX-02, is formulated as a solution for SC injection, containing 200 mg/mL. The placebo control will consist of a SC injection of normal saline at matching volumes.

The study includes at least 5 cohorts of 9 subjects each (both males and females need to be enrolled in each cohort, a significant number of female subjects needs to be enrolled). Subjects will be randomized to receive multiple doses of ELX-02 or placebo at a ratio of 2:1 in each cohort: Six subjects will receive ELX-02 and three will receive placebo:

Cohort 1: ELX-02 0.1 mg/kg or placebo SC twice a week for 9 doses;

Cohort 2: ELX-02 0.3 mg/kg or placebo SC twice a week for 9 doses;

Cohort 3: ELX-02 1.0 mg/kg or placebo SC twice a week for 9 doses;

Cohort 4: ELX-02 2.5 mg/kg (100 mg/mL) or placebo SC twice a week for 9 doses;

Cohort 5: ELX-02 up to 2.5 mg/kg (50 mg/mL) or placebo SC twice a week for 9 doses;

Cohort 6: ELX-02 2.5 to 5.0 mg/kg or placebo SC twice a week for 9 doses.

Cohort 7: ELX-02 up to 5.0 mg/kg or placebo SC twice a week for 9 doses.

Dose escalation to the next cohort will not be performed until after the 14-day observation period for the previous cohort, to allow for detection of unanticipated delayed AEs.

Changes to the planned dose may be made in any cohort, depending on safety and any available PK data. The dose will not exceed 5.0 mg/kg.

The assessments performed are summarized per visit in Table 1.

The study will comprise the following periods for each subject:

- A screening period, within 42 days before dosing up to Day -2 (including an ear, nose, and throat (ENT) exam with auditory and vestibular assessment up to Day -8).
  - An additional baseline ENT exam with auditory and vestibular assessment will be performed between Day -7 and Day -1. These assessments (screening and baseline) can be done on the same day (between Day -7 and Day -1) with 2-3 hrs between the 2 assessments.
- An in-house treatment and follow-up period consisting of a predose day (Day -1), dosing day (Day 1), and follow-up days (Days 2 and 3). Subjects will be released from the Clinical Pharmacological Unit (CPU) approximately 48h after dosing.

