Revised Protocol	15 May 2018	
 
Following recommendations of the local (Belgium) Health Authorities, a cohort for administration of a 5.0 mg/kg dose could be implemented in this MAD study after satisfactory safety results were obtained for this dose in the SAD study. Results from the SAD study evaluating the ELX-02 5.0 mg/kg and 7.5 mg/kg SC doses were added to Section 1.2.2. Given the favorable safety profile of the doses, a dose cohort of 5.0 mg/kg was added to this MAD study.
 
Glomerular filtration rate was only meant to be an inclusion criterion and was carried through the protocol inadvertently. Use of the eGFR estimated by the MDRD equation to monitor acute changes in renal function in a normal population is not appropriate and not indicated because the MDRD equation applies only to subjects with a GFR below 60 ml/min, can never be used to assess acute renal changes, and depends on an equation that smooths out many critical parameters. We are measuring serum creatinines and KIM-1 and clusterin as parameters of renal function. Therefore, assessment eGFR estimated by the MDRD equation was removed from visits after the screening visit.
 
Sponsor address was changed.
 

Revised Protocol	24 September 2018	
 
Injection site reactions (ISR) have been observed for all cohorts completed to date. The completed cohorts and number of ISR are as follows: 0.1 mg/kg (2 subjects with 2 ISR), 0.3 mg/kg (7 subjects with 10 ISR), 1.0 mg/kg (5 subjects with 41 ISR) and 2.5 mg/kg (7 subjects
 

Document	Version Date	Summary of Changes and Rationale

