1.2. Study Design

1.2.1. Synopsis of Study Design

This is a Phase 1, randomized, double-blind, placebo-controlled, third party open (i.e. pharmacist), multiple dose escalation study to evaluate the safety, tolerability and PK of SC administered ELX-02 in independent consecutive cohorts of healthy subjects.

The investigational drug, ELX-02, is formulated as a solution for SC injection, containing 200 mg/mL. The placebo control will consist of a SC injection of normal saline at matching volumes.

The study is designed to include at least 5 cohorts of 9 subjects each, including both males and females. Subjects will be randomized to receive multiple doses of ELX-02 or placebo at a ratio of 2:1 in each cohort; 6 subjects will receive ELX-02 and 3 will receive placebo for a total of up to 63 subjects. Study drug will be administered SC twice a week for 9 doses and dose levels planned in the protocol for each cohort are described below:

- Cohort 1: ELX-02 0.1 mg/kg or placebo
- Cohort 2: ELX-02 0.3 mg/kg or placebo
- Cohort 3: ELX-02 1.0 mg/kg or placebo
- Cohort 4: ELX-02 2.5 mg/kg or placebo
- Cohort 5: ELX-02 up to 2.5 mg/kg or placebo
- Cohort 6: ELX-02 2.5 to 5.0 mg/kg or placebo
- Cohort 7: ELX-02 up to 5.0 mg/kg or placebo

Dose escalation to the next cohort will not be performed until 14 days after the last subject's last dose in the previous cohort, to allow for detection of unanticipated delayed AEs.

The decision to proceed to a higher dose level will be following the recommendations of both the general Data Safety Monitoring Board (DSMB) and the Auditory and Vestibular Data Safety Monitoring Board (AVDSMB) based on the dose-escalation stopping rules. The DSMB and AVDSMB recommendation to proceed to a higher dose will be based on review of the blinded safety data, any available blinded PK data, and the results of audiologic tests and questionnaires. The next cohort will be dosed after the DSMB and AVDSMB have evaluated the available data and have recommended to escalate.

The principles of dose escalation, determination of dose limiting toxicity (DLT) and MTD, are detailed in Protocol Section 3.2.

Study duration will be approximately 12 weeks for each subject including a screening period of up to 6 weeks, treatment period of 4 weeks, and 2 weeks for final safety follow-up. Subjects will receive in-patient treatment in the Clinical Pharmacological Unit (CPU) for approximately 8 days throughout the treatment period.

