At the time this SAP was written, five doses have been investigated and two of the dose levels involved two different dilution schemes (different concentrations being injected), for a total of

seven cohorts. The final doses (ELX-02 injection solutions) administered in the study are summarized below:

- Cohort 1: ELX-02 0.1 mg/kg (50 mg/mL) or placebo
- Cohort 2: ELX-02 0.3 mg/kg (50 mg/mL) or placebo
- Cohort 3: ELX-02 1.0 mg/kg (100 mg/mL) or placebo
- Cohort 4: ELX-02 2.5 mg/kg (100 mg/mL) or placebo
- Cohort 5: ELX-02 1.0 mg/kg (50 mg/mL) or placebo
- Cohort 6: ELX-02 2.5 mg/kg (50 mg/mL) or placebo
- Cohort 7: ELX-02 5.0 mg/kg (50 mg/mL) or placebo.

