4.4.3. Adverse Events of Interest and Injection Site Reactions

Treatment-emergent AEOIs, defined per-protocol as hypersensitivity, nephrotoxicity, and ototoxicity, will be assessed. AEOIs, searched by the following standardized MedDRA queries (SMQs), will be summarized by PT: Hypersensitivity, Hearing and Vestibular Disorders, and Acute Renal Failure, as appropriate. The number and percentage of subjects with at least one AEOI as well as the number of AEOIs will be presented by treatment and dose and separately by concentration.

ISRs, defined per-protocol as pain or tenderness, erythema or redness, induration or swelling, and pruritus, and assessed by the investigators according to the Division of Acquired Immunodeficiency Syndrome (DAIDS) Criteria as described in Protocol Section 13.1 will be summarized by grade at each timepoint.

ISRs reported as spontaneous AEs that are coded with the high-level term (HLT) “Injection site reactions” will also be analyzed. The number and percentage of subjects with at least one ISR as well as the number of ISR events will be presented by treatment and dose and separately by concentration. The duration of each reported ISR will be derived using the AE dataset. The average duration of ISRs per subject will be summarized by treatment and dose and separately by concentration.

All AEOIs and ISRs occurring on-study as well as the duration of each observed ISR will be listed in by-subject data listings by cohort.

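### Injection site reactions are summarised against one pooled placebo column, so no planned table shows the volume-matched comparison that the design provides

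*SAP*

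**What the plan says.** Protocol 3.1 defines the control: "The placebo control will consist of a SC injection of normal saline at matching volumes". SAP 1.2.1 gives the allocation in each cohort: "6 subjects will receive ELX-02 and 3 will receive placebo for a total of up to 63 subjects". It also lists the doses and injected concentrations actually used, from "Cohort 1: ELX-02 0.1 mg/kg (50 mg/mL) or placebo" to "Cohort 7: ELX-02 5.0 mg/kg (50 mg/mL) or placebo".

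For the general and safety tables, SAP 3.2 states: "Placebo will be pooled across cohorts and presented in one column". SAP 3.5 repeats the pooling rule. SAP 4.4 applies the same layout (treatment and dose, then separately by concentration) to every safety tabulation. For ISRs reported as adverse events, SAP 4.4.3 says: "The number and percentage of subjects with at least one ISR as well as the number of ISR events will be presented by treatment and" (the sentence goes on to name dose level, and a second set of tables by concentration). Average ISR duration is handled in the same way, and solicited reactions are tabulated by DAIDS grade and timepoint.

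No summary uses injected volume or number of injections, and SAP 3.6 plans no covariate adjustment. Listings are by cohort (SAP 3.2), including the listing of ISRs and their durations (SAP 4.4.3).

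**The concern.** Matching placebo volume within a cohort separates the effect of the drug from the effect of injecting that amount of fluid. Pooling placebo over cohorts with very different volumes removes this separation from the summary tables. Volume rises with dose across the ELX-02 columns, while placebo appears as a single value. Any contribution of volume or number of injections to ISRs would then be read as drug effect and dose-response.

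ISRs matter here. Tolerability is a primary objective. The protocol's Document History (Section 13.4, entry for 24 September 2018) says that the accumulated ISRs at 2.5 mg/kg limited tolerability, and it gives the ISR experience as a reason for the added lower-concentration cohort.

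**Working it through.** **Plan's own figure.** 7 cohorts x 9 subjects = 63, which agrees with the stated maximum. Placebo: 7 x 3 = 21. ELX-02: 7 x 6 = 42.

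**Volumes.** The documents do not print volumes. They follow from volume per kg = dose (mg/kg) / concentration (mg/mL), using SAP 1.2.1. Placebo has the same volume by design.

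| Cohort | Dose (mg/kg) | Concentration (mg/mL) | Volume (mL/kg) |
|---|---|---|---|
| 1 | 0.1 | 50 | 0.002 |
| 2 | 0.3 | 50 | 0.006 |
| 3 | 1.0 | 100 | 0.010 |
| 4 | 2.5 | 100 | 0.025 |
| 5 | 1.0 | 50 | 0.020 |
| 6 | 2.5 | 50 | 0.050 |
| 7 | 5.0 | 50 | 0.100 |

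Range: 0.100 / 0.002 = 50-fold. At an assumed 70 kg this is 0.14 mL to 7.0 mL per dose.

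**Pooled placebo.** With 3 subjects per cohort the mean is (0.002 + 0.006 + 0.010 + 0.025 + 0.020 + 0.050 + 0.100) / 7 = 0.213 / 7 = 0.0304 mL/kg. Only 3 of 21 placebo subjects (14%) have the Cohort 7 volume.

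**Dose columns against that mean.** The 1.0 mg/kg column merges Cohorts 3 and 5; the 2.5 mg/kg column merges Cohorts 4 and 6.

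| Dose column (mg/kg) | Mean volume (mL/kg) | Ratio to pooled placebo |
|---|---|---|
| 0.1 | 0.002 | 0.07 |
| 0.3 | 0.006 | 0.20 |
| 1.0 | 0.015 | 0.49 |
| 2.5 | 0.0375 | 1.23 |
| 5.0 | 0.100 | 3.29 |

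Mean volume rises with every dose step. The ratios use volume per kg, so they need no assumed body weight.

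**What this could do to the table.** This part rests on assumptions, because the documents give no ISR rate by volume. Suppose there is no drug effect and that the proportion of subjects with an ISR is linear in log volume on the logit scale. Fix the proportions at 0.002 and 0.100 mL/kg and average over the seven cohorts for pooled placebo.

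| Assumed proportion, lowest to highest volume | Pooled placebo | 5.0 mg/kg minus pooled placebo (points) | 0.1 mg/kg minus pooled placebo (points) |
|---|---|---|---|
| 10% to 30% | 19.4% | +10.6 | -9.4 |
| 10% to 50% | 28.5% | +21.5 | -18.5 |
| 10% to 80% | 44.9% | +35.1 | -34.9 |
| 20% to 90% | 60.6% | +29.4 | -40.6 |

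Against placebo of the same cohort, the expected difference is 0 in every case. If volume has no effect, the expected distortion is 0 as well.

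**Concentration tables.** Cohort 5 against 3: 0.020 / 0.010 = 2. Cohort 6 against 4: 0.050 / 0.025 = 2. Volume and concentration change together at equal dose. The SAP does not say whether placebo in these tables means all 21 subjects or only those of Cohorts 3 to 6.

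**Precision.** The exact 95% upper limit for 0 events in n subjects is 1 - 0.025^(1/n): 71% for n = 3, 46% for n = 6, 34% for n = 9 and 16% for n = 21.

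**The case against.** **The matching is still in the data.** This stands. Because ISRs are listed by subject and cohort, a reader can rebuild each cohort's own comparison by hand. It would be wrong to infer that the trial has lost its volume-matched control. What is missing is a summary that shows it.

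**Nothing shows that volume causes ISRs.** This also stands. The Document History contrasts tolerability by concentration, not volume. It reports 2, 7, 5 and 7 affected subjects and 2, 10, 41 and 72 events at 0.1, 0.3, 1.0 and 2.5 mg/kg. The subject counts do not rise steadily with volume. If up to 1 mL goes into one injection (an assumption; Protocol 5.4 leaves this to the pharmacy manual), Cohorts 1 to 3 need one injection per dose at any eligible weight, yet events rose from 2 to 41. A fixed risk per injection does not explain that. Dose rises along with volume across these four cohorts, so the counts settle nothing.

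A reader might take "0.3 mg/kg (7 subjects with 10 ISR", with only 6 subjects per cohort assigned to ELX-02, as evidence of a volume effect. If the cohort had 9 subjects and none was replaced, at least 7 - 6 = 1 placebo subject was affected. That suggests a placebo background. It does not show that the background changes with volume.

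**Comparing the diluted regimen as given is legitimate.** Agreed: extra reactions from extra volume are part of the burden of that regimen, so total events must stay. A rate per injection answers a different question and cannot separate volume from concentration.

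**Three placebo subjects say little, and the stakes are descriptive.** True. No ISR test is planned, the study is exploratory, and escalation relied on board review after each cohort rather than on these tables. This limits the weight of the point. It does not justify showing only the unmatched comparison.

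**Conclusion.** The point holds as a conditional one. The planned ISR summaries set each dose column against placebo whose mean volume differs from its own, from about one fifteenth of the pooled placebo volume at 0.1 mg/kg to 3.3 times it at 5.0 mg/kg. If volume or number of injections contributes to ISRs, the tables would overstate the ELX-02 effect at 5.0 mg/kg, understate it at the low doses, and could present a volume effect as a dose-response.

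A reader might go further and infer that the tables do misstate the drug effect, or that the 50 mg/mL dilution will look worse only because more fluid was injected. The documents support neither. The volume ratios assume placebo volumes as planned and 3 placebo subjects per cohort. The percentage-point differences above are arithmetic under assumed rates, not forecasts. The consequence is a possible descriptive misreading of a primary tolerability finding, with no effect on a test or an error rate. A cheap improvement is warranted.

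**What to change.** Keep the pooled placebo column. In SAP 4.4.3, add one supplementary set of ISR summaries (solicited DAIDS grades, ISR adverse events, duration) that shows each cohort's ELX-02 subjects beside that cohort's own placebo.

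Alternatively, show placebo in narrow volume bands:

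- Cohorts 1-3: n = 9, 0.002 to 0.010 mL/kg
- Cohorts 4-5: n = 6, 0.020 to 0.025 mL/kg
- Cohorts 6-7: n = 6, 0.050 to 0.100 mL/kg

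The lowest band still spans 5-fold and the highest 2-fold, so the by-cohort display is the cleaner match.

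For the 50 against 100 mg/mL tables:

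- State that placebo comes from the same cohorts.
- Give ISR events per injection given alongside total events, not in their place.
- Add a footnote that volume and concentration change together.

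The denominator should be the injections actually given. Protocol 5.4 has the details of each administration recorded. The nine injections per subject in SAP 4.4.1 count dosing occasions, whereas Protocol 5.4 allows several injections per dose.

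The cost is SAP wording and a few extra columns, with no new assessments. The drawback is imprecision, so the tables should be labelled descriptive.
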